8 ASSESSMENT OF EFFICACY

8.1 Specification of the Efficacy Parameters

Initial disease assessment of patients should be performed within 28 days prior to the first dose of study drug using computed tomography (CT) and/or magnetic resonance imaging (MRI). This scan will be considered as baseline scan. The PI should review baseline scan images to confirm the subject has measurable disease as defined in the inclusion criteria. Scan performed as part of routine clinical management is acceptable for use as the baseline scan if it is of diagnostic quality and performed within 28 days prior to the C1D1, or as approved by the medical monitor if it is out of window period.

Subsequent scan (CT and/or MRI as applicable) should be done at C3D1 (± 7 days) and approximately 8 weeks thereafter (± 7 days), and/ or at the EOT and so on or as clinically indicated (if clinical progression is suspected). If a CR or PR is noted, confirmatory scans should be performed at least 4 weeks after the initial response was first documented. The scan should be reviewed by site investigator/radiologist/designee and tumour response will be assessed according to the revised Response Evaluation Criteria in Solid Tumour guideline (RECIST) version 1.1.[21]

8.2 Images included in the assessment.

A CT with IV contrast will be the primary modality for assessment, unless the patient has an allergy to contrast that cannot be controlled with pre-medications. If patients are unable to receive iodinated CT contrast, the preferred imaging is non-contrast CT of the chest, and MRI of the abdomen and pelvis with contrast. Tumour imaging should remain consistent throughout study and should include those thought by investigator to best capture status of disease. For skin nodules, CT or MRI will be the preferred modality of assessment. Digital photography will not be acceptable as a method of assessment for skin lesions.

8.3 Measurable and non-measurable disease:

Eligibility of lesions for quantitative assessment will be determined at baseline, with target lesions selected from the measurable lesions identified. After baseline, target lesions will always be assessed quantitatively, and non-target lesions will be assessed qualitatively, with no further evaluation of measurability according to these definitions.

8.3.1 Measurable Disease

A lesion is considered measurable, if it meets one of the measurability criteria described above.

CONFIDENTIAL Page 50 of 66

- A lesion is considered measurable if it has a diameter of ≥ 10 mm in the axial plane on CT or MRI, assuming that the slice thickness is 5 mm or less. If the slice thickness is greater than 5 mm, the minimum size increases to two times the slice thickness.
- Pathological lymph nodes are considered measurable if the short axis (greatest dimension perpendicular to the longest diameter) is ≥ 15 mm at baseline.
- Skin nodules will be considered measurable lesion if they are assessed on CT or MRI.
 Digital photography will not be acceptable as a method of assessment for skin lesions.
 Discrete skin nodules that are not visible on CT or MRI should be considered non-measurable lesions.
- Bone lesions that are lytic or mixed lytic-blastic, which have soft tissue components seen on CT or MRI, and which meet size criteria above, may be measurable.
- Cystic metastases may be considered measurable, but solid lesions are preferred for selection as target.

8.3.2 Non-Measurable Disease

A lesion is considered non-measurable, if it does not meet the measurability criteria described above. Example of non-measurable lesion included.

- A lymph node that has a short axis diameter of 10-14 mm is considered evaluable, but not measurable. Nodes with a short axis diameter of < 10 mm are considered normal.
- Palpable skin nodules that are not discernible using CT or MRI are considered evaluable but not measurable for this study.
- Bone lesions that are blastic are non-measurable.
- Simple cysts are considered benign by default.
- Malignant ascites or pleural/pericardial effusions, lymphangitic infiltration of skin or lung, leptomeningeal disease, inflammatory breast disease, and infiltrative disease without clear borders.
- Lesions seen on bone scan, or modalities other than CT or MRI (plain X-ray [with the exception for lung lesions], PET etc.) cannot be measured. These modalities can be used only to determine whether a lesion is present or absent.
- Previous local treatment: A previously irradiated lesion (or lesion subjected to other local treatment) is non-measurable unless it has progressed since completion of previous treatment.

8.4 Baseline Lesion Selection and Documentation

Target lesions will be chosen from among the measurable lesions. The lesions chosen should be the largest, most reproducible, and most representative of the overall disease distribution.

- Target lesions: All measurable lesions up to a maximum of 5 lesions total, and 2 lesions per organ, should be selected as target lesions. Paired organs (lungs, kidneys, adrenals, ovaries) are considered one organ. The lymph nodes collectively are considered one organ.
- **Non-nodal target lesions** are measured in the longest diameter in the axial plane (on CT or MR). Malignant lymph nodes are always measured in the short axis diameter (greatest dimension perpendicular to the longest diameter). The appropriate measurements for all

CONFIDENTIAL Page 51 of 66

target lesions chosen at baseline will be added to produce the recorded sum of diameters, which will be recorded.

• Other disease present at baseline should be recorded as 'Non-target lesions'.

8.5 Assessment of Response

The overall response for each visit is a combination of target lesion response, non-target lesion response, and the presence or absence of new lesions. **Target lesions measurements** should be performed in the same manner as at baseline. The sum of diameters of all target lesions must be calculated and compared to the baseline value and to the nadir value (the smallest value previously seen during the trial, which may be the same as baseline). The following special rules apply to lesion measurements:

- If two target lesions coalesce the longest diameter measurement of the coalesced mass is used. If a large target lesion splits, the longest diameter of each fragment is measured, and the sum is used.
- Measurements for target lesions that become small should continue to be recorded, as long as the investigator is confident in the accuracy. If a target lesion is considered to have completely disappeared, 0 mm should be recorded. If it is too small to measure accurately, but is still present, a default value of 5 mm should be recorded.
- When nodal lesions decrease to < 10 mm (normal), the actual measurement should still be recorded.

Target lesion response categories are defined as follows:

- Complete response (CR): Disappearance of all non-nodal target lesions. Target lymph nodes must reduce to < 10 mm in short axis.
- Partial response (PR): At least a 30% decrease in the sum of diameters of target lesions, compared to the sum at baseline.
- Progressive disease (PD): At least a 20% increase in the sum of target lesion measurements, compared to the smallest sum on study (including baseline). Also, the absolute increase in the sum has to be at least 5 mm.
- Stable disease (SD): If none of the above criteria meets.

Non-target lesion response assessment is qualitative. Categories are defined as follows:

- CR: Disappearance of all non-nodal non-target lesions. Non-target lymph nodes must reduce to < 10 mm in short axis. Note: If tumour markers are initially above the upper normal limit, they must normalize for a patient to be considered in complete clinical response.
- PD: Unequivocal progression of non-target lesions, evaluated as a whole, such that it is clear that treatment has failed, and disease is progressing, regardless of the status of the target lesions.
- Non-CR/Non-PD: Neither CR nor PD criteria are met.

New lesion response is classified as present or not ("Yes" or "No"). The response is "Yes" if there is at least one lesion that the investigator considers unequivocal new tumour.

CONFIDENTIAL Page 52 of 66

- Lesions that are equivocal (for example, due to small size) should not be considered new until they are confirmed by later scanning. Once confirmed, they can be retrospectively called new lesions at the time they were first seen.
- A lesion identified in an area not previously scanned is considered a new lesion.
- New lesions seen on nuclear medicine bone scans should be confirmed using anatomical imaging, whenever possible. If bone lesions are confirmed on later CT or MRI scan, progression should be assigned to the visit in which new lesion(s) were first seen on bone scan (in a manner similar to other equivocal new lesions). In the absence of structural confirmation, the pattern of lesions must clearly indicate metastasis, usually with at least two new lesions present.

Overall response is determined by combining the target, non-target, and new lesion responses.

| Table 9 | : | Response | Assessment |
|---------|---|----------|-------------------|
|---------|---|----------|-------------------|

| Target Lesions | Non-Target Lesions | New Lesions | Overall Visit Response |
|-----------------------|---------------------|-------------|---------------------------|
| CR | CR | No | CR |
| CR | Non-CR/Non-PD or NE | No | PR |
| PR | Non-CR/Non-PD or NE | No | PR |
| SD | Non-CR/Non-PD or NE | No | SD |
| PD | Any | Yes or No | PD |
| Any | PD | Yes or No | PD |
| Any | Any | Yes | PD |

After all visits have been evaluated, the sequence of overall visit responses is used to derive best overall response (BOR).

- BOR is defined as the best visit response recorded from the start of the treatment until disease progression/recurrence.
- ORR: It is defined as sum of CR and PR rates
- Clinical Benefit Rates: It is defined as sum of CR, PR and SD rates
- PFS is measured from the time of first dose of study drug to radiographic (or tumour marker as applicable) documentation of disease progression or death due to any cause.

9 STATISTICAL METHOD AND CONSIDERATIONS

9.1 General Considerations

This section describes the statistical methods to be used to analyze efficacy and safety. These methods may be revised and updated due to reasons such as regulatory requirements or need for further clarifications. All statistical analyses will be performed using SAS 9.1 or higher. The final analysis plan will be documented in a formal statistical analysis plan (SAP) that must be finalized before database lock. The SAP will include details on how variables will be derived, how missing data will be handled, and how data will be presented as well as the details on statistical methods to be used for safety and efficacy analyses. The final clinical study report will discuss deviations from the SAP, if any.

CONFIDENTIAL Page 53 of 66

9.2 Determination of Sample Size

A sample size of 20 per group will provide a precision of 13% for a two-sided 90% confidence interval based on Exact (Clopper-Pearson) method assuming the percentage of patients without progression at the end of 6 month is 20%. Thus, total 40 patients (20 patients in each group) will be enrolled in the study.

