| | - Any other situation where in the opinion of the investigator, continued | | | |
| | participation in the study would not be in the best interest of the patient. | | | |
| | | | | |
| | In addition, patients will be discontinued from the study in the following | | | |
| | circumstances: | | | |
| | - Consent withdrawal by the patient (all patients are free to withdraw from | | | |
| | participation in this study at any time, for any reasons, specified or unspecified, | | | |
| | and without prejudice). | | | |
| | PregnancyNon-compliance by study patient. | | | |
| | - Confirmed disease progression during therapy. | | | |
| | - Discontinuation of the study by the Sponsor | | | |
| | , , | | | |
| Safety | AEs will be recorded and graded according to National Cancer Institute Common Terminology Criteria for Adverse Events (NCI-CTCAE version 5.0). Physical | | | |
| assessment: | examination, vital signs, ECGs and clinical laboratory tests will be performed at | | | |
| | screening and at specific time points during the study. Clinical and laboratory | | | |
| | evidence of AEs will be monitored routinely throughout the study and for 30 days | | | |
| | following discontinuation of the study drug. | | | |
| | ronowing discontinuation of the study drug. | | | |

CONFIDENTIAL Page 9 of 66

| Computed tomography (CT) with IV contrast will be the primary modality for assessment, unless the patient has an allergy to contrast that cannot be controlled with pre-medications. If patients are unable to receive iodinated CT contrast, the preferred imaging is non-contrast CT of the chest, and MRI of the abdomen and pelvis with contrast. Disease will be re-assessed by the site investigator/radiologist using RECIST version 1.1 at C3D1 (± 7 days) and approximately 8 weeks thereafter (± 7 days), and/or at the EOT and/or as clinically indicated (if clinical progression is suspected). Investigator-assessed response will be used for analysis. |
|---|
| A sample size of 20 per group will provide a precision of 13% for a two-sided 90% |
| confidence interval based on Exact (Clopper-Pearson) method assuming the percentage of patients without progression at the end of 6 months is 20%. Thus, a total of 40 patients (20 patients in each group) will be enrolled in the study. |

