5.2 Changes from the Analyses Planned in the Protocol

There were no changes in the analysis planned in the protocol of the study at the time of preparing this statistical analysis plan.

BASELINE, EFFICACY and Safety EVALUATIONS 6.

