8.7.1 Analysis of Primary Efficacy Variable

The primary endpoint will be analysed to assess the anti-tumour activity of tenalisib in patients with locally advanced or metastatic breast cancer.

The summary of patients without disease progression at the end of 6 months will be provided by frequency and percentage along with 95% confidence intervals of these percentages for both the treatment groups. The 95% confidence intervals of these percentages will be calculated using exact method based on binomial distribution.

The efficacy analysis will also be summarized by metastasis type (de novo metastasis, recurrent metastasis) and overall.

> Page 16 of 106 ST-AD-032 version 01

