A patient with two or more prior non-drug treatments in the same system organ class (or with the same preferred term) is counted only once for that system organ class (or preferred term).

System organ classes are sorted in alphabetical order. Preferred terms are sorted within system organ class by descending order of frequency of overall preferred terms.

Prior non-drug treatments are those that were taken only prior to the first dose of study drug.

Reference Listing 16.2.x.x

Document Date: 12MAY2023.

Protocol RP6530-2101 Table 14.1.5.4 Summary of Concomitant Non-Drug Treatments Safety Analysis Set Page xx of yy

System Organ Class	Tenalisib 800 mg BID	Tenalisib 1200 mg BID	Overall
Preferred Term	(N=XX)	(N=XX)	(N=XX)
	n (%)	n (%)	n (%)
Patients with at least one Concomitant	xx (xx.x)	xx (xx.x)	xx (xx.x)
Non-Drug Treatment			
SOC1	xx (xx.x)	xx (xx.x)	xx (xx.x)
PT1	xx (xx.x)	xx (xx.x)	xx (xx.x)
PT2	xx (xx.x)	xx (xx.x)	xx (xx.x)
Etc.			

Percentages are based on the total number of patients (N) in each treatment group.

A patient with two or more concomitant non-drug treatments in the same system organ class (or with the same preferred term) is counted only once for that system organ class (or preferred term).

Non-drug treatments are coded using MedDRA (version 24.0).

System organ classes are sorted in alphabetical order. Preferred terms are sorted within system organ class by descending order of frequency of overall preferred terms.

Concomitant non-drug treatments are those that were taken while on study drug. The non-drug treatments that started after the discontinuation of study drug will also be termed as 'Concomitant non-drug treatments'

Reference Listing 16.2.x.x

Document Date: 12MAY2023.

Protocol RP6530-2101

Table 14.2.1.1

Summary of Patients Without Disease Progression at the End of 6 Months

ITT Analysis Set

	Tenalisib 800 mg BID	Tenalisib 1200 mg BID	Overall
	(N=xx)	(N=xx)	(N=xx)
Number (%) of patients without progression at the End of 6 months 95% CI*	xx (xx.x)	xx (xx.x)	xx (xx.x)
	(xx.x, xx.x)	(xx.x, xx.x)	(xx.x, xx.x)

The Intent - to - Treat (ITT) analysis set includes all patients who received at least 1 dose of study medication.

Percentages are based on the total number of patients (N) in each treatment group.

At 6 months, patients with treatment duration ≥180 days are summarized.

Reference Listing 16.2.x.x

Document Date: 12MAY2023

Program: xx.sas Table Generation: ddmmmyyyy hh:mm:ss

Use same format for

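### The 13% precision that justifies 20 patients per group is only the shorter, lower arm of the two-sided 90% exact interval, and at the 95% level the SAP reports it holds on neither side

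*Protocol*

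**What the plan says.** Three places carry the same sizing statement: the protocol synopsis, Protocol 9.2 and SAP 4.5. Each says: "A sample size of 20 per group will provide a precision of 13% for a two-sided 90% confidence interval based on Exact (Clopper-Pearson) method". The assumed proportion without progression at 6 months is 20%, and the conclusion is 20 patients in each of two groups, 40 in all. Precision is not defined in any of them. There is no power calculation, null rate or decision rule.

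For the analysis, Protocol 9.4.3 lists the primary endpoint without a confidence level; it sets 95% for ORR and CBR. SAP 8.7.1 sets the level for the primary endpoint: "The 95% confidence intervals of these percentages will be calculated using exact method based on binomial distribution". The shell for Table 14.2.1.1 agrees, with the row "Number (%) of patients without progression at the End of 6 months 95% CI". No analysis section or table shell plans a 90% interval. SAP 5.2 states: "There were no changes in the analysis planned in the protocol of the study at the time of preparing this statistical analysis plan".

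**The concern.** There are two separate problems.

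First, a single precision figure attached to a two-sided interval is normally read as plus or minus that figure. An exact binomial interval around 20% with 20 patients is far from symmetric, so one number cannot describe it unless the text says which number it is. If 13 is the distance to one limit only, the reader has been given the favourable side and not told so.

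Second, the SAP sizes the study on a 90% interval and reports a 95% one, which is wider. The interval that justified the sample size is never reported, and nothing connects the two levels.

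This matters because precision is the only property claimed for 20 per group. Protocol 1.5.2 intends the study to help choose between the two doses, so how well each group's rate can be estimated is what a reader needs to know. Someone who takes the 13% at face value expects about 2 × 13 = 26 points from limit to limit.

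**Working it through.** **Inputs.** From Protocol 9.2: n = 20 per group, assumed proportion 20% (so x = 4), two-sided 90%, Clopper-Pearson. From SAP 8.7.1: 95%, exact binomial.

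**Formula.** With α equal to 1 minus the confidence level:

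- lower limit = α/2 quantile of Beta(x, n − x + 1) = Beta(4, 17)
- upper limit = 1 − α/2 quantile of Beta(x + 1, n − x) = Beta(5, 16)

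**Step 1: reproduce the plan's figure (90%, α/2 = 0.05).** The limits are 7.14% and 40.10%.

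- Distance to the lower limit: 20 − 7.14 = 12.86, which rounds to 13.
- Distance to the upper limit: 40.10 − 20 = 20.10.
- Half-width: (40.10 − 7.14)/2 = 16.48.

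The stated 13% is therefore recovered, but only as the estimate minus the lower limit.

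**Step 2: could 13 be some other half-width?** At 90% with n = 20 and 20%, the half-widths in points are:

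- Wald: 1.645 × √(0.2 × 0.8/20) = 14.71
- Wald with continuity correction: 17.21
- Wilson: 14.26
- Agresti-Coull: 14.65
- mid-P: 14.77
- Clopper-Pearson half-width averaged over a Binomial(20, 0.2) outcome: 15.94

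None rounds to 13. An exact 80% interval has half-width 13.52, which rounds to 14 and is not the stated level.

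**Step 3: the level the SAP reports (95%, α/2 = 0.025).** The limits are 5.73% and 43.66%.

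| Exact interval, 4/20 | Limits | Below 20% | Above 20% | Half-width | Full width |
|---|---|---|---|---|---|
| 90% (sizing) | 7.1% to 40.1% | 12.9 | 20.1 | 16.5 | 33.0 |
| 95% (SAP analysis) | 5.7% to 43.7% | 14.3 | 23.7 | 19.0 | 37.9 |

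At 95% neither arm is as short as 13.

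**Step 4: separate the two effects.**

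- Quoting only the lower arm at 90% understates the half-width by 16.48 − 13 = 3.5 points, and the upper arm by 20.10 − 13 = 7.1 points.
- Moving from 90% to 95% adds 14.27 − 12.86 = 1.4 points to the lower arm, 23.66 − 20.10 = 3.6 to the upper arm, and 18.96 − 16.48 = 2.5 to the half-width.

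**Step 5: scale.** Checking n in steps of 5 at an observed 20%, a half-width that rounds to 13 first appears at 30 per group for 90% (13.31) and 40 per group for 95% (13.30). This shows the size of the gap; it is not a proposal to enrol more patients. Pooling both groups (8/40) gives a 95% half-width of 13.30, but the plan states its figure per group and at 90%.

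**The case against.** The best defence is that 13% is not a miscalculation. It is the correct distance to the lower limit, and half-width is only one convention for precision, which the plan never says it adopts. Method, level, n and assumed rate all stand in the same statement, so a reader can recompute the interval. The first part is right: this is a labelling fault, not an arithmetic slip. But the label is attached to an interval expressly called two-sided, the arm quoted is the shorter one, and the other arm is about 7 points longer. Having to recompute the interval to learn its precision defeats the purpose of stating it.

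On the confidence level, the protocol sets none for the primary endpoint. The synopsis and Protocol 9.1 leave method details to the SAP, and 95% matches the level used for ORR and CBR. So the SAP contradicts no analysis instruction in the protocol, and its statement of no changes is not false on this point. That stands. What remains is that SAP 4.5 and SAP 8.7.1 use different levels in one document without comment.

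It can also be said that restating the sizing at 95% rewrites the original rationale, and that the SAP, dated 12 May 2023, already records in 5.1 that the study closed early. This bears on how the correction is worded. It does not make the existing sentence accurate.

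**Conclusion.** The concern holds. At the assumed 20% with 20 patients, the two-sided 90% exact interval spans 33.0 points with a half-width of 16.5, and the reported 95% interval spans 37.9 points with a half-width of 19.0. The plan's wording leads a reader to expect 26 points and 13. The 13% describes the lower arm alone at 90%, and neither arm at 95%.

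These figures rest on exactly 4 of 20 patients being without progression, which is the plan's own assumption; the interval will differ at other observed counts. No estimate, test or decision threshold depends on the 13%, and the results table will show the actual interval. The point should be fixed because precision is the sole justification offered for the sample size. It does not threaten the validity of the analysis.

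**What to change.** In the protocol synopsis, Protocol 9.2 and SAP 4.5, replace the precision sentence with the full expected interval at the level used for analysis. For example: with 20 per group and 4/20 without progression at 6 months, the exact two-sided 95% CI is 5.7% to 43.7% (−14/+24 points). If the sponsor wants to preserve the original basis, the 90% interval can be given beside it, with both limits.

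Alternatively, keep 90% throughout: state 7.1% to 40.1% (−13/+20 points) and change SAP 8.7.1 and Table 14.2.1.1 to 90%.

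Either way, add one line in SAP 5.2 recording which level applies to the primary endpoint and that the sizing used 90%. Word it as a clarification, since the protocol set no level for that endpoint.

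The cost is wording in three places and one added line; the second option also changes the level in SAP 8.7.1 and the table shell. Enrolment, endpoint and interval method stay as they are. The only downside is that the stated precision looks less favourable.
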